		Attachment representation measured by YP report: AAQ (Bodfield et al., 2020)
		YP self-efficacy measured by YP report: NGSE (Chen et al., 2001)
		CU traits measured by YP and parent report: CU Traits MAP; (Hawes et al., 2020)
		Temperamental irritability measured by YP report: ODD subtyping DSM items (Stringaris & Goodman, 2009)
		YP School attendance and truancy measured by parent report; and YP report from ISRD4

		Age; gender; ethnicity; SES; household composition; parent relationship to YP measured by parent and/or YP report (this includes some demographic data). Service being seen; days from first caseworker contact to randomisation measured by administrative data	
Baseline for	variable	Delinquency	
primary outcome	measure (instrument, scale, source)	Measured by YP report: International Self-Report Delinquency Study 4 survey offending scale (ISRD4; Marshall et al., 2022)	
	variable	YP mental health and adjustment; Child Criminal Exploitation; substance misuse; parental mental health; parental monitoring and supervision; family functioning; parental self-efficacy; attachment representation; YP self-efficacy; Callous-Unemotional (CU) traits; temperamental irritability; school attendance and truancy; age; gender; ethnicity; SES; household composition; service being seen; parent relationship to YP; days from first caseworker contact to randomisation.	
	measure (instrument, scale, source)	YP mental health and adjustment measured by Parent and YP report: Strengths and Difficulties Questionnaire (Goodman, 2005)	
Baseline for secondary outcome		Child Criminal Exploitation measured by YP report: SRD4 additional items.	
		Substance Misuse measured by YP report: ISRD3 substance misuse subscale.	
		Parental mental health measured by parent report: DASS-21 (Henry & Crawford, 2005)	
		Parenting supervision, knowledge and YP disclosure measured by YP report: ISRD3.	
		Family Functioning measured by YP and parent report: SCORE-15 (Fay et al., 2013)	
		Parental self-efficacy measured by parent report: BPSES (Woolgar et al., 2023)	
		Attachment representation measured by YP report: AAQ (Bodfield et al., 2020)	

YP self-efficacy measured by YP report: NGSE (Chen et al., 2001)

CU traits measured by YP and parent report: CU Traits MAP (Hawes et al., 2020)

Temperamental irritability measured by YP report: ODD subtyping DSM items (Stringaris & Goodman, 2009)

YP School attendance and truancy measured by parent report; and YP report from ISRD4

Age; gender; ethnicity; SES; household composition; parent relationship to YP measured by parent and/or YP report

Service being seen; days from first caseworker contact to randomisation measured by administrative data

Sample size calculations overview

Sample size calculations are not determined on the basis of a priori MDES but rather results from the pilot RCT.

		Protocol	Randomisation
Pilot study Effect Size		g = 0.36 [-0.32,1.03]	
Pre-test/ post- test correlations	level 1 (participant)	0.523	
Alpha ⁶		0.05	
Power		0.8	
One-sided or two-sided?		One sided	

⁶ Please adjust as necessary for trials with multiple primary outcomes, 3-arm trials, etc., when a Bonferroni correction is used to account for family-wise errors.

9

			Protocol	Randomisation
Number of participants		Intervention	144	
	of	Control	144	
	Total	288		

Sample size estimates for a full efficacy RCT were calculated using clincalc.com and checked against G^* Power calculations. Estimates used 80% power and p = 0.05 with an enrolment ratio of 1. Power calculations used one-sided tests because there is no recorded case of FFT having iatrogenic effects.

The primary outcome in the efficacy study is *Offending*: Self-reported delinquency (SRD) - International Self-Report Delinquency Study 4 survey offending scale (ISRD4; Marshall et al., 2022). This was not the primary outcome in the pilot study. Whilst a number of trials of FFT have been conducted with offending as a primary outcome, and a previous trial of FFT-G did include delinquency as a primary outcome, it recruited court mandated youth who were offending. The focus of the pilot was instead YP at risk of criminal exploitation recruited from social care.

Therefore, the anticipated primary outcome in the pilot study was CCE as recorded on agency systems. During the pilot study, it became clear that this was not recorded reliably and so two co-primary outcomes collected directly from participants were used instead: PCG reported family functioning (total scale score) and YP reported conduct problems (CP; subscore of the SDQ). As a result, power calculations for this efficacy trial did not make use of SRD data from the pilot study. Based on the effect size for PCG-reported Family Functioning outcome in the pilot study (g = 0.36 (-0.32,1.03)), clincalc.com returned 238 participants, increased to 288 to account for up to 10% loss to follow-up at each assessment time point. Based on the effect size for YP-reported CP (g = 1.15 (0.13,1.52)), clincalc.com returned 42 participants, increased to 51 to account for 10% loss to follow-up at each assessment time point. After discussion with the YEF Assistant Director of Evaluation, the decision was taken to use the upper end of this sample size calculation range (N=288). Any harmful effects will be monitored through serious incident reporting. The pre-test/post-test correlation also mirrors the results of the pilot trial (i.e., 0.523).

However, as subsequently requested by the YEF, this trial will use self-reported delinquency as the primary outcome. The rationale for this is:

- A core YEF strategic aim is to understand what works to reduce crime and violence, so YEF aims to select offending as the primary outcome in all YEF studies where it is plausible that the intervention will reduce it, e.g. it is included in the theory of change
- The primary outcome must be measured using a valid and reliable measure and there were no valid and reliable measures of other relevant outcomes that are highly connected to crime e.g. child criminal exploitation.
- The mitigations included since the pilot study to increase the chance of seeing impact on offending (e.g. screening YP, introducing anonymous reporting of outcomes by YP)
- The co-primary outcomes from the pilot study will be included as secondary outcomes so that it will still be possible to test for intervention effects on these.

Participants

Participants will be YP between 10-17 at risk of CLDN involvement or CCE being seen by child social care or related agencies in three London local authorities and their primary caregiver (PCG).

Inclusion criteria - YP and families

We use broader criteria identified by the Child Safeguarding Practice Review Panel (2020) for CCE/CLDN involvement, with a view to further screening undertaken subsequently in consultation:

Child/ young person aged between 10–17 years

AND

ONE OR MORE OF:

Known to services due to concerns in the last 12 months around:

Child sexual exploitation (CSE)

Child criminal exploitation (CCE)

Missing (from home or care) episodes

Potential or actual gang or CLDN affiliation as identified by police or other statutory service

Repeated school exclusion or absence

Involvement as a perpetrator or victim of youth violence or criminality

OR

TWO OR MORE OF THE FOLLOWING (OVER THE LAST 12 MONTHS):

Family conflict or inadequate supervision

Associating with antisocial peers

Concerns about alcohol or drug use

AND EITHER

Index child/young person is living at home 50% or more each week.

OR

Index child/young person is currently in an out of home placement, but with a clear return home plan (discussed on a case-by-case basis).

AND

Caregiver(s) and index child/young person are willing to engage in family therapy.

Exclusion criteria - YP and families:

- Index child/young person is actively homicidal, suicidal or psychotic.
- Problem sexual behaviour is the central concern.
- Presence of organic and/or cognitive conditions that may have prevented family members making use of talking therapy.
- Key family members, defined as "major players" in FFT-G, refuse family-based therapy.
- Significant child protection concerns: basic needs of children are not being met.
- Family have plans to move out of borough, thereby making therapy unfeasible within five months.

Analysis

We will test the effect of FFT-G on primary and secondary outcomes on an intention-to-treat basis using hierarchical linear mixed modelling, with post-treatment and baseline outcomes, trial arm and trial arm by time interaction term as explanatory variables (included in power calculations). Linear mixed models allow repeated measures from each participant to be correlated by fitting random intercepts varying at the level of the individual, thereby improving the precision of estimates. We will analyse differences in treatment outcomes in subgroups (e.g., by gender, age, temperamental irritability, CU traits and presence of offending behaviour at baseline identified by caseworker) by using interaction terms. We will

calculate effect sizes for primary and secondary outcomes. We will use structural equation modelling to test for mediators of treatment (which are listed as secondary outcomes above).

Based on evidence from the pilot trial it is possible that some outcome variables may be skewed, in particular the primary outcome. We will determine whether transformation or scaling is appropriate depending on the skew and distribution of the data.

The analytical approach has been determined a priori and will be conducted with R Studio and SPSS.

Primary outcome analysis

The primary outcome is the ISRD4 total score which is a continuous variable. All YP will complete this measure at baseline, 6 months after randomisation and 12 months after randomisation. The main test of treatment effect will be at 12 months after randomisation. The total score uses a sum of the total volume of delinquent acts using 14 questions. The response scale for each question can be from 0 to whatever the total number of acts reported is (although see above for transformation approach). A hierarchical linear mixed model will be used with site as a fixed effect.

Regression models will be adjusted by the baseline number of offences in the six months prior to randomisation and stratification factors; age group and site, as covariates. The regression model specification is detailed in eq. 1.

Eq. 1

OFF6i,j = α + β 1 (allocation)i,j + β 2 (OFF0)i,j + β 3 (age)i,j + β 4 (site)j + β 4 (study)j ϵ

Secondary outcome analysis

The secondary outcomes are:

- YP Child Criminal Exploitation measured by items added to the Self-Report Delinquency Scale (YP report).
- YP Substance Misuse measured by ISRD3 substance misuse subscale (YP report).
- YP Conduct Problems measured by the conduct problems subscale of the SDQ (YP and parent report).
- YP mental health and adjustment measured by total score and impact score on the SDQ (YP and parent report; impact score parent report only).
- Parental mental health measured by the DASS-21 (parent report).

We will add three additional questions to the SRDS scale asking about missing from home episodes, storing or transporting drugs or weapons and engaging in sexual activity in exchange for money or goods. For each of these additional questions and for each of the 14 SRDS questions we will ask whether anyone has tried to involve the YP in these behaviours, who they were and how many times this happened. The CCE scale will be calculated from the total volume of how many times they were involved by others in these 17 behaviours and will range from 0 to the total number reported (although see above for transformation approach).

The ISRD3 substance misuse scale asks about the use of 5 substances, with response options varying depending on the substance. The scale can be from 0 to whatever the total number of times substances were used is (although see above for transformation approach). In addition, we will add questions on use of synthetic substances and on non-prescribed medications. We will calculate an additional total scale with these additional items and this will be analysed separately from the main ISRD3 substance misuse subscale.

SDQ subscales, including the conduct problems subscale, contain 5 items scored 0, 1 and 2, with scale values from 0 to 10. The SDQ total difficulties scale ranges does not include the prosocial scale and therefore ranges from 0 to 40. The impact score is computed by summing questions on distress and impairment and ranges from 0 to 10.

The DASS-21 contains 21 items, 8 for each of the anxiety, depression and stress subscales, with response values of 0, 1, 2 and 3. We will calculate the total score which ranges from 0 to 63.

All secondary outcome scores are treated as continuous, and a hierarchical linear mixed model will be used with site as a fixed effect. As noted above, we will determine whether transformation is appropriate depending on the data.

Subgroup analyses

Any subgroup analyses will be exploratory in nature. Sample size calculations for the trial have been conducted on the basis of the main primary outcome analysis, not for subgroup analyses. Therefore, it is possible that subgroup analyses may be underpowered. We will conduct post-hoc power analyses when all data has been collected and frame our reporting of these analyses accordingly. Analyses will be conducted using interaction terms.

The subgroup analyses proposed in the protocol were differences in gender, age, temperamental irritability, CU traits and presence of offending behaviour at baseline as identified by caseworker.

We aim to conduct the following analyses

- Race: we will explore whether FFT was equally effective with YP and parents from
 minoritised backgrounds as for those from White backgrounds. Specifically, we would
 expect to compare those of Black backgrounds to those of White backgrounds and
 compare those of South Asian backgrounds to those of White backgrounds. This is on
 the basis that those from minoritised backgrounds may face more structural
 challenges that may impede the impact of FFT-G.
- Age: we will explore whether age moderates the effect of FFT using a continuous measure of age. We may expect that FFT-G may work better for those who are younger and therefore at an earlier age of their criminal careers.
- Gender: we will explore whether FFT is as effective with YP who identify as female as much as with those who identify as male. We are unlikely to have an adequate sample size to include those who do not identify as male or female in these analyses so will use a dichotomous measure of gender. As FFT-G has been predominantly developed, delivered and evaluated with males we may expect less impact on females.
- Callous-Unemotional (CU) Traits: we will explore whether the presence of CU traits moderates the effect of treatment. Specifically, we would hypothesise that YP with elevated CU traits would be less responsive to treatment. CU traits will be measured with the CU Traits MAP, consisting of 4 items with a total scale of 0 to 12.
- Temperamental Irritability: we will explore whether the presence of temperamental irritability moderates the effect of treatment. Specifically, we would hypothesise that YP with elevated irritability would be more responsive to treatment. Temperamental irritability will be measured with 3 items from the SDQ and ODD subtyping items, with a total scale of 0 to 9.
- Offending at baseline: we will explore whether FFT reduces self-reported delinquency more in YP whose referring practitioner reported that they were offending at baseline compared to those who reported to not be offending at baseline. This will use a dichotomous score.

Further analyses

These analyses were planned after the protocol, but before the commencement of the trial. We will explore potential mediators of treatment using Structural Equation Modelling. These analyses will be exploratory in nature. Sample size calculations for the trial have been conducted on the basis of the main primary outcome analysis, not for mediation analyses. Therefore, it is possible that mediation analyses may be underpowered. We will conduct post-

hoc power analyses when all data has been collected and frame our reporting of these analyses accordingly.

We will test the following mediators:

- Parental supervision, knowledge and child disclosure, measured by ISRD3 subscales, 12 items, scale ranges from 0 to 48.
- Family functioning measured by SCORE-15, 15 items, scale ranges from 15 to 75.
- Attachment representation using the AAQ, 9 items, scale ranges from 0 to 36.
- Parental self-efficacy measured by the BPSES, 5 items, 5 to 15.
- YP self-efficacy using the NGSE, 8 items, scale ranges from 8 to 40.

We would anticipate conducting analyses comparing the explanatory power of individual YP vs. parent/family factors in predicting mediation of treatment effect, covarying for baseline values of outcomes.

Interim analyses and stopping rules

We do not plan to conduct interim analyses. We will monitor data completion and missing data rates and monitor and report adverse events. The trial will stop if the YEF, FPM and the University of Greenwich decide that the trial is unable to recruit a sufficient number of participants.

Longitudinal follow-up analyses

No longitudinal analyses other than those to test treatment effects will be conducted.

Imbalance at baseline

We will produce a table of baseline characteristics by trial arm, including age, ethnicity, gender, school attendance, CU traits, temperamental irritability, offending at baseline and outcomes. We will report means and standard deviations and counts and percentages with histograms of baseline data. We will not formally test for imbalance at baseline but will address any effects of potential imbalance using the missing data strategy specified below.

Missing data

We will report on rates of missing data of all measures by treatment group. We will use logistic regression models to identify predictors of missingness and include these as covariates in analyses of outcomes described above. If levels of missing data warrant it, we will consider

imputation techniques but the precise techniques used will depend on the pattern and extent of missingness. We will comply with the YEF Guidance on Missing Data.

Compliance

We use FFT LLC's own guidance of defining and measuring family compliance with the intervention. This stipulates that the total dose will depend on the needs of the family. However, we will report on the number of families who attended at least one session, and consider how many families moved through how many phases of treatment, how many received a critical dose of 8 sessions, mean number of sessions received and how many were deemed to have completed treatment. We will also report on therapist fidelity to the FFT model. This data will be provided by FFT LLC using the clinical monitoring system completed by FPM therapists. We will also explore whether time from referral to first FFT session is associated with compliance and improvement in outcomes. If power permits, we will explore whether compliance and fidelity are associated with improvements in the primary outcome and in CCE and SDQ conduct problems.

As advised by the YEF Statistical Guidance we will use an Instrumental Variable approach. This will use a Two Stage Least Square Analysis guidance (2SLS) approach with group allocation as the instrumental variable for the compliance indicator. Results for the first stage will be reported alongside with i) the correlation between the instrument and the endogenous variable; and, ii) a F test.

Intra-cluster correlations (ICCs)

This is not applicable to the current trial.

Presentation of outcomes

Effect sizes will be calculated using Hedges' g. Hedges' g is specified using the following formula:

```
Hedges' g = (x1 - x2) / V((n1-1)*s12 + (n2-1)*s22) / (n1+n2-2) where:
```

x1, x2: The sample 1 mean and sample 2 mean, respectively

n1, n2: The sample 1 size and sample 2 size, respectively

s12, s22: The sample 1 variance and sample 2 variance, respectively

The confidence interval for the Hedge's g statistic is:

g±φ - 1 (1-(α /2))gse where:

 ϕ - 1 = the percent point function of the normal distribution

gse= the standard error of the g statistic

 $= \sqrt{(n1+n2)/n1n2 + g^2/2(n1+n2)}$

References

We will add in to revised version.

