Two co-primary outcomes were used: PCG reported family functioning (total scale score) and YP reported conduct problems (CP; subscore of the SDQ). Based on the effect size for PCG-reported Family Functioning outcome ($g = 0.36$ (-0.32,1.03)), clincalc.com returned 238 participants, increased to 288 to account for up to 10% loss to follow-up at each assessment time point. Based on the effect size for YP-reported CP ($g = 1.15$ (0.13,1.52)), clincalc.com returned 42 participants, increased to 51 to account for 10% loss to follow-up at each assessment time point. After discussion with the YEF Assistant Director of Evaluation, the decision was taken to use the upper end of this sample size calculation range (N=288). Any harmful effects will be monitored through serious incident reporting.

Table 2: Sample size calculation

		PARAMETER
Pilot study Effect Size		$g = 0.36$ [-0.32,1.03]
Pre-test/ post-test correlations	level 1 (participant)	0.523
Alpha ⁹		0.05
Power		0.8

⁹ Please adjust as necessary for trials with multiple primary outcomes, 3-arm trials, etc., when a Bonferroni correction is used to account for family-wise errors.

		PARAMETER
One-sided or two-sided?		One sided
Number of participants	Intervention	144
	Control	144
	Total	288

Outcome measures

Details on primary and secondary outcomes and other variables are provided below. Table 3 provides contextual information on the outcomes relating to offending and CCE.

Outcome data collection points

There are three data collection points: at baseline prior to randomisation; post-treatment: six months after randomisation; follow-up: twelve months after randomisation.

Unless specified below, all measures will be collected by a University of Greenwich researcher at all time points.

Table 3: Outcome terminology

Terminology	
Offending behaviours	Offending behaviours refer to behaviours that break the law. The YEF refer to three types of offending behaviours: (a) non-violent crime (viz. that do not involve violence against another person such as shoplifting, graffiti, using illegal drugs); (b) sexually violent crime; and (c) violent crime against another person (e.g., assault, robbery using threat or force, homicide)

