Number of adults in the house (parent report)

Number of children/YP in the house (PCG report)

Service the YP was seeing (administrative data)

PCG relationship to YP (PCG report)

Number of days from first contact with a caseworker (typically consultation) and randomization (administrative data)

All collected at baseline only.

Compliance¹²

Data on treatment compliance is captured as routine clinical monitoring on the FFT CCS system and will be provide by FFT LLC (the developers) and FPM (the grantee delivering the FFT-G). This will include:

¹² Compliance here is equivalent to the broader term adherence.

Number of sessions received

Phases completed

Critical dose (8 session or more) delivered or not

Fidelity to the intervention model

FFT-LLC therapist and client outcome measures

Therapeutic alliance

Analysis

We will test the effect of FFT-G on primary and secondary outcomes on an intention-to-treat basis using hierarchical linear mixed modelling, with post-treatment and baseline outcomes, trial arm and trial arm by time interaction term as explanatory variables (included in power calculations). Linear mixed models allow repeated measures from each participant to be correlated by fitting random intercepts varying at the level of the individual, thereby improving precision of estimates. We will analyse differences in treatment outcomes in subgroups (e.g., by gender, age, temperamental irritability, CU traits and presence of offending behaviour at baseline identified by caseworker by using interaction terms). We will calculate effect sizes for primary and secondary outcomes. We will use structural equation modelling to test for mediators of treatment (see measures above). Please see IPPE section below for planned analysis of compliance data.

Longitudinal follow-ups

The effect of treatment will be assessed both 6 months after randomisation (at the end of treatment) and 12 months after randomisation (6 months after treatment ends). We will use the latter timepoint as the main assessment of treatment effects. See above for analytical models.

Implementation and process evaluation

Overview

This section presents information about the implementation and process evaluation (IPE). We would aim to deliver a mixed-methods IPE alongside of the Efficacy Study.

The rest of this section covers:

- Research questions
- Research methods

- Approach to analysis

Research questions

This IPE has been designed in line with YEF guidance on IPEs.

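### The Analysis sentence lists the 6-month outcome as an explanatory variable for a 12-month test and conflicts with Eq. 1; neither text coherently specifies the 12-month primary contrast

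*SAP*

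**What the plan says.** The general model is described in almost identical words in the Analysis section of each document. The SAP lists the explanatory variables as "with post-treatment and baseline outcomes, trial arm and trial arm by time interaction term as explanatory variables (included in power calculations"; the protocol has "with post-treatment and baseline outcomes, trial arm and trial arm by time interaction term as explanatory variables". The next SAP sentence adds: "Linear mixed models allow repeated measures from each participant to be correlated by fitting random intercepts varying at the level of the individual".

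The protocol (Outcome data collection points) fixes the terms: "post-treatment: six months after randomisation; follow-up: twelve months after randomisation". The primary time is the later one. The SAP (Primary outcome analysis) says "The main test of treatment effect will be at 12 months after randomisation", and the protocol (Longitudinal follow-ups), after naming both assessments, says "We will use the latter timepoint as the main assessment of treatment effects".

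The SAP's Primary outcome analysis section then gives a different specification: "Regression models will be adjusted by the baseline number of offences in the six months prior to randomisation", together with age group and site. Its only equation begins "OFF6i,j = α + β 1 (allocation)i,j + β 2 (OFF0)i,j + β 3 (age)i,j" and continues with site and study terms. The post-treatment outcome is not on its right-hand side.

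**The concern.** The 6-month outcome is measured after randomisation, at the end of treatment, and FFT-G is meant to change it. If it is a covariate in the model for the 12-month outcome, the arm coefficient no longer estimates the total intention-to-treat effect that research question 1 asks for. It estimates what is left after the part already visible at 6 months has been adjusted away.

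The rest of the SAP does not settle the matter. The SAP says that its approach was fixed in advance, yet its two descriptions of the primary model differ in response, covariates and terms. An analyst could follow either one, and they estimate different things.

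**Working it through.** **1. The two texts side by side**

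| | Analysis sentence (SAP, protocol) | SAP Eq. 1 and adjustment sentence |
|---|---|---|
| Response | not stated | labelled OFF6; label not defined |
| 6-month outcome as covariate | yes, as worded | no |
| Baseline outcome | explanatory variable | covariate (OFF0) |
| Time, arm-by-time | arm-by-time | neither |
| Participant random intercept | yes | none shown |
| Age, site | not mentioned | yes |

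The main test is at 12 months. The Analysis sentence does not name the 12-month outcome, and Eq. 1 carries a label that reads as month 6.

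**2. The plan's own sample size**

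Inputs from the SAP, Sample size calculations overview: g = 0.36, alpha 0.05, power 80%, one-sided, stated result 238, raised to 288. The formula is n per arm = 2(z_alpha + z_power)² / g².

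- One-sided: 2(1.645 + 0.842)² / 0.1296 = 95.4, so 96 per arm and 192 in total.
- Two-sided: 2(1.960 + 0.842)² / 0.1296 = 121.2, so 122 per arm and 244 in total.
- With baseline adjustment, multiply by 1 − 0.523² = 0.726: 140 one-sided, 178 two-sided.

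The stated 238 is close only to the two-sided, unadjusted comparison (within 3%). The remark that the model terms were included in the power calculation therefore does not show which model was meant.

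**3. Effect of conditioning on the 6-month outcome**

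Inputs:
- 12-month effect d12 = 0.36 SD. This is the plan's figure, taken from caregiver-reported family functioning in the pilot, not from offending.
- Correlation of baseline with each later outcome: 0.523 (the plan's figure, applied to both times).
- 12-month completers: 288 × 0.81 = 233.
- Assumed, because the documents do not give them: the 6-to-12-month correlation r and the 6-month effect d6.

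Formulas:
- Coefficient on the 6-month outcome given baseline: b6 = (r − 0.523²) / (1 − 0.523²).
- Arm coefficient: d12 − b6 × d6.

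Central case, r = 0.523 and d6 = 0.36:
- b6 = (0.523 − 0.2735) / 0.7265 = 0.343.
- Arm coefficient = 0.36 − 0.343 × 0.36 = 0.236, which is 34% lower.
- Residual variance = 1 − 2 × 0.523 × 0.343 = 0.641.
- SE, allowing for the arm difference in the covariate = √[0.641 × 4/233 × (1 + (0.36²/4)/0.7265)] = 0.107.
- Power = Φ(0.236/0.107 − 1.645) = 71% one-sided; with 1.960, about 60% two-sided.

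Baseline adjustment only: SE = √(0.7265 × 4/233) = 0.112 and 0.36/SE = 3.22, so power is 94% one-sided or 90% two-sided.

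A simulation of 5,000 trials of 232 participants under the central assumptions gives a conditioned coefficient of 0.233, with power of 70% one-sided and 59% two-sided.

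**4. Sensitivity, varying one assumption at a time**

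| r | d6 | Arm coefficient | Loss | One-sided power |
|---|---|---|---|---|
| 0.523 | 0 | 0.360 | 0% | 96% |
| 0.523 | 0.18 | 0.298 | 17% | 88% |
| 0.523 | 0.36 | 0.236 | 34% | 71% |
| 0.523 | 0.50 | 0.188 | 48% | 53% |
| 0.3 | 0.36 | 0.347 | 4% | 92% |
| 0.6 | 0.36 | 0.198 | 45% | 62% |
| 0.7 | 0.36 | 0.149 | 59% | 49% |
| 0.8 | 0.36 | 0.099 | 72% | 35% |

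**The case against.** The strongest reply is that the sentence is loose drafting and that the context shows a repeated-measures model. If the 12-month outcome were the only response, each participant would contribute one row, and neither the arm-by-time term nor the random intercept could be estimated. The protocol also wants effects at both 6 and 12 months from the same models, and a 6-month effect cannot come from a model that uses the 6-month outcome as a covariate. Eq. 1 and the adjustment sentence leave that outcome out.

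All of this stands, and it limits the point in two ways. A reader might infer that the planned model conditions away much of the treatment effect. The documents do not support this: the more specific SAP section contradicts it, and the size of any loss rests on two quantities that the plan does not give. A reader might also infer that, with repeated responses, the test becomes a less precise change-from-baseline contrast. The documents do not support that either, because the SAP adjusts for baseline as a covariate.

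The reply does not supply a usable model, however. If the phrase about post-treatment and baseline outcomes names the responses, the 12-month outcome is missing from it. Eq. 1 has one outcome occasion, labelled OFF6, and no time or arm-by-time term, so as written it does not give the 12-month contrast. The label might refer to a six-month recall period, but the SAP does not say so, and its counterpart OFF0 is the baseline value.

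**Conclusion.** Wrong as written. The Analysis sentence in both documents names a post-randomisation outcome as an explanatory variable for a later primary effect. It conflicts with Eq. 1, and Eq. 1 does not specify the 12-month contrast either. This conclusion rests on the text alone and needs no assumption.

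The numerical consequence is conditional on someone following the sentence literally. With equal effects at both times and all correlations at 0.523, about a third of the effect is lost, and one-sided power falls from 94% to about 71%. Varying one assumption at a time, the loss runs from 0% to about 72%. These figures show what the wording could cost. They do not predict the result of this trial, and the 0.36 is not an effect on offending.

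**What to change.** Replace the Analysis sentence in the SAP and the protocol, and rewrite Eq. 1, so that all three state one model. For participant i at time t = 6, 12 months:

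OFF(i,t) = α + β1 arm(i) + β2 T12(t) + β3 arm(i) × T12(t) + β4 OFF0(i) + β5 age(i) + site(i) + u(i) + ε(i,t)

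Here T12 marks the 12-month occasion, site is a fixed effect and u(i) is the participant random intercept. State that:

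- the 6- and 12-month outcomes are responses, and the 6-month outcome is never a covariate;
- the single primary estimate is the arm contrast at 12 months, β1 + β3, with the 6-month contrast β1 reported as secondary;
- the study term in the present Eq. 1 is either defined or deleted, and each coefficient has its own label (β4 now appears twice).

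The cost is one paragraph in each document and one equation, with no change to data collection or sample size. It should be done before the separately held offending data are linked to the main study data, which the protocol places at the end of the study.
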